• For subjects of groups DTN and DTC, an AE is considered treatment emergent for **Cycle 1** if the start date is on or after the date of delayed treatment at Week 8.

All other AEs are considered to be non-TEAEs (i.e., all AEs with start date prior to initial injection).

An overall AE summary table will be provided by treatment cycle or overall as appropriate, displaying the following content:

- Any AEs;
- Any non-TEAEs;
- Any TEAEs;
- Any related TEAEs;
- Any TESAEs;
- Any related TESAEs;
- Any TEAEs leading to discontinuation from study; and/or
- Any TEAEs leading to discontinuation of study treatment.

For TEAEs, related TEAEs, TESAEs, and related TESAEs, number of subjects with TEAEs and number of TEAEs will be summarized by SOC and PT, by treatment cycle or overall as appropriate.

In addition, the following TEAE incidences will be shown by treatment cycle or overall as appropriate:

- TEAEs, number of subjects with TEAEs by PT;
- TEAEs by worst intensity, number of subjects with TEAEs by SOC and PT;
- TEAEs by worst causal relationship, number of subjects with TEAEs by SOC and PT;
- TEAEs by worst outcome, number of subjects with TEAEs by SOC and PT; and
- TEAEs by maximum duration, number of subjects with TEAEs by SOC and PT (duration categories: 1 to 3 days, 4 to 7 days, 8 to 14 days, 15 to 28 days, and > 28 days).

Duration of TEAEs will be calculated by the difference of start and stop date plus 1 day.

Moreover, the AE overview table as well as incidences of related TEAEs (by PT and SOC) will be provided for the following subgroups, by treatment cycle:

- Touch-up (yes/no) (applies to Cycle 1 only);
- Gender; and
- Fitzpatrick skin types (I, II, III and IV, V, VI).

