6.2.1 Adverse Events

All AEs will be coded according to the Medical Dictionary for Regulatory Activities (MedDRA) version in effect at the time the database is locked.

In the electronic case report form (eCRF), AEs will be reported with their onset and information on study discontinuation (tick box "AE leading to Discontinuation of the Study" = "Yes") and treatment discontinuation (tick box "Action taken with Medical Device" = "Treatment suspended"). The start date of the AE will be the date of the record reporting the onset of the AE and the stop date will be the stop date or ongoing, if not yet resolved. For seriousness, intensity, causal relationship, and outcome the worst attributes of each AE will be documented. The worst outcome is defined in the following order (from best to worst):

- recovered/resolved
- recovered/resolved with sequelae
- recovering/resolving
- not recovered/not resolved
- unknown
- fatal.

TEAEs are defined as AEs with onset at or after the first administration of study treatment. The handling of missing start and stop dates are described in TEAEs will be assigned to a treatment cycle (see treatment cycles in Section 6) based on the following rules:

- For subjects of treatment groups TN or TC (and TRT), TEAEs will be grouped into two treatment cycles according to the AE onset date, as follows:
 - For subjects without retreatment:

An AE is considered treatment emergent for Cycle 1 if the start date of the AE is on or after the date of the initial treatment injection.

o For subjects with retreatment:

An AE is considered treatment emergent for Cycle 1 if the start date of the AE is on or after the date of the initial injection and before the date of retreatment.

An AE is considered treatment emergent for Cycle 2 if the start date of AE is on or after the date of the retreatment. In case of any doubts because of exact day or time of onset information missing, an AE will be rather be assigned to Cycle 2 than to Cycle 1.

• For subjects of groups DTN or DTC (and DTRT), an AE is considered treatment emergent for **Cycle 1** if the start date is on or after the date of delayed treatment at Week 8.

All other AEs are considered to be non-TEAEs (i.e., all AEs with start date prior to initial injection).

For TEAEs, an overall summary table will be provided, displaying the following content by treatment cycle and overall:

- Any TEAEs;
- Any related TEAEs;
- Any TESAEs;
- Any related TESAEs;

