- Any TEAEs leading to discontinuation from study;
- Any related TEAEs leading to discontinuation from study;
- Any TEAEs leading to discontinuation of study treatment;
- Any related TEAEs leading to discontinuation of study treatment;
- Any fatal TEAEs and
- Any fatal TEAEs related to treatment.

For TEAEs, related TEAEs, TESAEs, non-serious TEAEs, TEAEs leading to discontinuation from study and related TESAEs, number of subjects with TEAEs and number of TEAEs will be summarized by SOC and PT for each treatment cycle and overall. TESAEs, TEAEs leading to discontinuation from study and related TESAEs will only be summarized if more than 5 subjects (over all treatment groups) experienced such a TEAE.

In addition, the following TEAE incidences will be shown overall and by treatment cycle:

- Number of subjects with TEAEs by PT;
- Number of subjects with TEAEs by worst intensity, by SOC and PT;
- Number of subjects with TEAEs by worst causal relationship, by SOC and PT;
- Number of subjects with TEAEs by worst outcome, by SOC and PT; and
- Number of subjects with TEAEs by maximum duration, by SOC and PT (duration categories: 1 to 3 days, 4 to 7 days, 8 to 14 days, 15 to 28 days, and > 28 days);
- Number of subjects with related TEAEs by worst intensity;

Number of subjects with related TEAEs by maximum duration (duration categories: 1 to 3 days, 4 to 7 days, 8 to 14 days, 15 to 28 days, and > 28 days);

Moreover, a summary of all related TEAEs will be provided, summarizing the number of events by severity and by duration.

The duration of TEAEs will be calculated by the difference of start and stop date plus 1 day. Missing start and stop days will be imputed as described in **ECLEPHICAL** If a TEAE is ongoing at study end, TEAE duration will be calculated as the difference between TEAE start date and last contact date + 1.

Moreover, the TEAE overview tables as well as incidences and number of related TEAEs (by PT and SOC) will be provided for the following subgroups, overall and by treatment cycle:

[figure not shown]
- Baseline MIHAS (2 vs. 3);
- Race (white vs. other);
- Ethnicity (Hispanic or Latino vs. not Hispanic or Latino);
- Age (< 45 years vs. ≥ 45 years);
- Touch-up (yes/no) (applies to Cycle 1 only);
- Sex; and
- Fitzpatrick skin type (I, II, III vs. IV, V, VI).

[figure not shown]

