For all randomized subjects, a summary table presenting the number and percentage of subjects who experienced any AE at any time during study and the number and percentage of subjects with any non-TEAEs will be displayed by randomized treatment groups (TRT, CDTRT) and overall. This analysis will use subjects as randomized and will be based on all randomized subjects.

Additionally, AEs reported for subjects in the CTL group from date of randomization until Week 8 (pre-injection) will be summarized separately showing number of subjects with AEs and number of AEs by system organ class (SOC) and preferred term (PT). For subjects who received treatment at Week 8, AEs that started on the day of injection will not be considered in this analysis. For subjects who never received treatment, all AEs until end of study will be considered.

Listings for related TEAEs, TEAEs leading to study discontinuation, serious TEAEs, and serious TEAEs leading to death will be provided in the corresponding table section. For related TEAEs, AEs with delayed onset will be flagged. A delayed onset AE is defined as an AE with an onset more than 28 days after the most recent injection (i.e., the latest injection prior to the AE onset).

All AEs including non-TEAEs, as well as all reported device deficiencies, will be listed with all details recorded in the listings section.

Disposition of subjects

The number of subjects screened will be provided. Other subject disposition information (i.e., number of subjects randomized, treated and re-treated, as well as the number of subjects in each analysis population) will be summarized by treatment group and overall (TRT, CDTRT and TOTT) and additionally by treatment group and injection technique (needle/cannula) and overall (TN, TC, CDTN, CDTC, and TOTT). Similar descriptive analyses will be performed by site in a separate table.

The absolute and relative frequencies for subject's main reason for premature study discontinuation will be tabulated overall and separately for discontinuations before/at Week 8 and after Week 8 for various treatment groups (TN, TC, TRT, CDTN, CDTC, CDTRT and TOTT), based on all randomized subjects.

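### TEAEs still ongoing at last contact that began no more than 27 days earlier are tabulated as completed events of 28 days or less

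*SAP*

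**What the plan says.** SAP 6.2.1 gives the general rule: "The duration of TEAEs will be calculated by the difference of start and stop date plus 1 day". For an event without a stop date it adds: "If a TEAE is ongoing at study end, TEAE duration will be calculated as the difference between TEAE start date and last contact date", again plus 1 day. SAP section 6, in defining treatment cycles, equates study end with the date of last contact, so the rule also covers subjects who leave early.

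The result feeds three outputs in SAP 6.2.1:

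- subjects with TEAEs by maximum duration, by SOC and PT;
- the table described as "Number of subjects with related TEAEs by maximum duration";
- a summary of all related TEAEs that counts events by severity and by duration.

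The classes stated for the two subject-level tables are "duration categories: 1 to 3 days, 4 to 7 days, 8 to 14 days, 15 to 28 days, and > 28 days". No class, flag or footnote for ongoing events is stated.

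The status itself is captured. In the same section, "the stop date will be the stop date or ongoing, if not yet resolved". Protocol 13.4.2 also records unresolved events as ongoing, but its only duration rule is "Duration of TEAEs will be calculated by the difference of start and stop date plus 1 day". The rule for ongoing events therefore comes from the SAP alone.

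**The concern.** For an event that has not resolved, the time from onset to last contact is the least its duration can be. The SAP enters that minimum as the duration. A subject whose swelling began on Day 2, and who was last seen on Day 15 with the swelling still present, is counted with the subjects whose swelling lasted 8 to 14 days and then resolved.

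Duration is part of how this product's safety is described. Protocol 6.2 says that earlier injection-site responses cleared within two weeks, and that a cannula may prolong local irritation by 1 to 2 days compared with a needle. SAP 6.2 reports safety by injection technique, so readers will use these tables to judge both statements.

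The rule also sits oddly with SAP 6.4.1. There, missing AE intensity is set to severe and missing causality to related, as a worst case. An ongoing event instead receives the shortest duration compatible with what was observed.

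**Working it through.** The plan states no figure to reproduce here, so the check applies the SAP rule to every possible onset day.

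**Inputs**

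- Duration rule and categories: SAP 6.2.1.
- Target day of the final visit, counted from the relevant injection: Day 505 (treatment groups, no retreatment), Day 337 (delayed treatment, visit C7) and Day 169 (after retreatment). Source: visit-window tables in SAP 6.4.1.
- Earlier target days, used to represent early leavers: Days 15, 29 and 57, from the same tables.

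**Formula.** Let S be the onset day and L the last contact day. The assigned duration of an ongoing event is D = L − S + 1.

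**Which ongoing events are affected.** D ≤ 28 requires L − S ≤ 27, that is, onset on the last contact day or in the 27 days before it. By category the exposed onset days number 3 (1 to 3 days), 4 (4 to 7), 7 (8 to 14) and 14 (15 to 28). Their sum is 3 + 4 + 7 + 14 = 28. If L − S ≥ 28, then D ≥ 29 and the event falls above 28 days. That class has no upper limit, so the placement is right however long the event goes on.

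**Share of possible onset days, Day 1 to Day L, that give D ≤ 28**

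| Last contact (day after injection) | Exposed days | Share |
|---|---|---|
| 15 | 15 of 15 | 100% |
| 29 | 28 of 29 | 96.6% |
| 57 | 28 of 57 | 49.1% |
| 169 | 28 of 169 | 16.6% |
| 337 | 28 of 337 | 8.3% |
| 505 | 28 of 505 | 5.5% |

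These are shares of calendar days, not of events. Onset is unlikely to be uniform over time, and the documents do not say how many TEAEs will be ongoing.

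**Worked case: onset Day 2, never resolved**

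- L = 15: D = 15 − 2 + 1 = 14, shown as 8 to 14 days.
- L = 29: D = 29 − 2 + 1 = 28, shown as 15 to 28 days.
- L = 30: D = 30 − 2 + 1 = 29, shown as more than 28 days, which is correct.
- L = 57: D = 57 − 2 + 1 = 56, shown as more than 28 days, which is correct.

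The exposure is therefore concentrated in subjects lost within about four weeks of an injection, and in late-onset events close to the final visit.

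**The case against.** The strongest reply is that little is lost.

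- **Completers.** An event that starts soon after injection and persists to the final visit is already above 28 days. This stands, and it is why the point is confined to a 28-day window.
- **Unresolved status is reported elsewhere.** The SAP plans "Number of subjects with TEAEs by worst outcome, by SOC and PT", with outcome levels for events still resolving or not resolved. Related TEAEs are listed in the table section, and "All AEs including non-TEAEs, as well as all reported device deficiencies, will be listed with all details recorded in the listings section". A reader can find the unresolved events. However, no listed table crosses outcome with duration, so the duration tables remain uncorrected.
- **Follow-up.** Protocol 9.2.6.2 asks sites to try to follow unresolved non-serious AEs beyond the final visit, and Protocol 9.2.5 asks for repeated contact attempts and last-visit assessments. This reduces the number of ongoing events but cannot help for subjects who are lost.
- **Unseen material.** The mock tables that SAP section 1 uses as output specifications are not among the documents, and the reference for imputing missing dates is not legible. An ongoing row or footnote may exist there. The visible text nevertheless states an explicit rule that assigns a duration, and an unseen layout does not override it.
- **Descriptive only.** No hypothesis test and no incidence endpoint depends on the rule. This is correct and limits the weight of the point.

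A reader might infer that unresolved events in general are shown as short, or that reported durations are always shortened. The documents support neither. Ongoing events with earlier onset are classed correctly. An event inside the window is also classed correctly if it goes on to resolve before crossing the next category boundary.

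**Conclusion.** The point holds for a limited set of events: TEAEs ongoing at last contact with onset on that day or in the 27 days before it. For these, SAP 6.2.1 reports a right-censored duration as a completed one of 28 days or less. Any misclassification is toward shorter duration.

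The number affected is probably small and cannot be derived from the documents. It depends on how many subjects leave soon after an injection with an open event, and on how many events begin shortly before the final visit. The conclusion assumes that the duration tables follow the visible SAP text.

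It would go too far to infer that the plan conceals unresolved events, since outcome and listings both show them. This is a minor improvement to descriptive safety tables, worth making because it is cheap.

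**What to change.** In SAP 6.2.1, add a row to the TEAE and related-TEAE duration tables and to the related-event summary by duration: *ongoing at last contact, observed 28 days or less*. Do not give these events a completed-duration category. Ongoing events observed for more than 28 days stay in the top class.

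Two of the tables count subjects by maximum duration, so a precedence rule is needed. Count a subject:

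1. in the class above 28 days if any event exceeds 28 days;
2. otherwise in the ongoing row if any event is ongoing;
3. otherwise in the longest completed category.

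For example, a subject with one event ongoing after 5 days and another resolved after 20 days goes in the ongoing row. Where a table is split by SOC and PT, apply the rule within each line.

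The cost is one extra table row, a short precedence rule in the SAP, and slightly fewer events shown as short. No new data are needed, because ongoing status is already recorded.

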8 CLINICAL INVESTIGATION PLAN

8.1 Overview of Study Design

This is a prospective, multicenter, randomized, comparative, evaluator-blinded pivotal study designed to evaluate the safety and effectiveness of BBL for the correction of volume loss in the IOH. Study subjects will have a screening period of up to 10 days and participate for a maximum duration of 76 weeks (\pm 14 days).

A total of 150 subjects will be randomized at up to 9 investigational sites in the United States (US). At each study site, the number of subjects randomized should not exceed 26. A minimum of 20% of enrolled subjects will be Fitzpatrick Skin Type IV, V, or VI Subjects from the Fitzpatrick Skin Type IV, V, or VI group will be distributed as follows: at least 16 subjects of Type IV; 7 subjects of Type V; and 7 subjects of Type VI. At least 10% of the subjects enrolled will be male.

Subjects eligible for study enrollment will have symmetrical right and left IOHs with the same MIHAS score of 2 or 3 (moderate or severe), as assessed live by a blinded evaluator. All blinded evaluators will be qualified healthcare practitioners, delegated by the treating investigator and trained by the sponsor. At screening, eligible subjects will be randomized to 4 groups using a 2:2:1:1 ratio as follows: BBL with needle (TN), BBL with cannula (TC), control/delayed-treatment BBL with needle (CDTN), and control/delayed-treatment BBL with cannula (CDTC). The needle or cannula assignment for a subject cannot be interchanged during the study; that is, needle and cannula cannot be used in the same subject.

Subjects randomized to treatment will receive a BBL injection in both IOHs at Day 1. Treated subjects who do not achieve optimal aesthetic correction or at least 1-point improvement on the MIHAS, as assessed by the blinded evaluator 4 weeks post treatment compared to baseline, may have a touch-up injection in one or both IOH(s). If a touch-up is necessary, it will only be administered if there are no medical contraindications or existing AEs of concern, as determined by the treating investigator. The treating investigator will be responsible for reviewing whether the threshold for optimal aesthetic correction or at least 1-point MIHAS improvement is met, as assessed by the blinded evaluator, since the blinded evaluator will not have access to the subject's study records.

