2.1 Clinical Study Design

This is a prospective, multicenter, randomized, comparative, evaluator-blinded pivotal study designed to evaluate the safety and effectiveness of Belotero Balance[®] (+) Lidocaine (BBL) for the correction of volume loss in the Infraorbital Hollow (IOH) area. Study subjects will have a screening period of up to 10 days and participate for a maximum duration of 76 weeks (\pm 14 days).

A total of 150 subjects will be randomized at 9 investigational sites in the United States (US). At each study site, the number of subjects randomized should not exceed 26. A minimum of 20% of enrolled subjects will be Fitzpatrick Skin Type IV, V, or VI. Subjects from the Fitzpatrick Skin Type IV, V, or VI group will be distributed as follows: at least 16 subjects of Type IV; 7 subjects of Type V; and 7 subjects of Type VI. At least 10% of the subjects enrolled will be male.

Subjects eligible for study enrollment will have symmetrical right and left IOHs with the same Merz Infraorbital Hollow Assessment Scale (MIHAS) score of 2 or 3 (moderate or severe), as assessed live by a blinded evaluator. All blinded evaluators will be qualified healthcare practitioners, delegated by the treating investigator and trained by the sponsor. At screening, eligible subjects will be randomized to 4 groups using a 2:2:1:1 ratio as follows: BBL with needle (TN), BBL with cannula (TC), control/delayed-treatment BBL with needle (CDTN), and control/delayed-treatment BBL with cannula (CDTC). The needle or cannula assignment for a subject cannot be interchanged during the study; that is, needle and cannula cannot be used in the same subject.

Subjects randomized to treatment (TN or TC) will receive a BBL injection in both IOHs at Day 1. Treated subjects who do not achieve optimal aesthetic correction or at least 1-point improvement on the MIHAS, as assessed by the blinded evaluator 4 weeks post treatment compared to baseline, may have a touch-up injection in one or both IOH(s). If a touch-up is necessary, it will only be administered if there are no medical contraindications or existing adverse events (AEs) of concern,

as determined by the treating investigator. The treating investigator will be responsible for reviewing whether the threshold for optimal aesthetic correction or at least 1-point MIHAS improvement is met, as assessed by the blinded evaluator, since the blinded evaluator will not have access to the subject's study records.

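### The Cycle 1 TEAE table by touch-up (yes/no) counts events from before the touch-up and sorts subjects partly by their adverse events, so it cannot show what the touch-up adds; an onset-based table should sit beside it

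*SAP*

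**What the plan says.** SAP 6.2.1 (Adverse Events) states, for each cycle as well as for the whole study, that "the TEAE overview tables as well as incidences and number of related TEAEs (by PT and SOC) will be provided for the following subgroups". One of the seven subgroups is "Touch-up (yes/no) (applies to Cycle 1 only"). Protocol 13.4.2 plans the same split.

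The Cycle 1 window in SAP 6.2.1 opens at the first injection in every case:
- treatment groups with retreatment: "if the start date of the AE is on or after the date of the initial injection and before the date of retreatment";
- treatment groups without retreatment: "if the start date of the AE is on or after the date of the initial treatment injection";
- delayed-treatment groups: "if the start date is on or after the date of delayed treatment at Week 8".

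Touch-up comes later. Under SAP 2.1, subjects short of the target "4 weeks post treatment compared to baseline, may have a touch-up injection in one or both IOH(s"). Protocol 8.1 adds that "it will only be administered if there are no medical contraindications or existing AEs of concern, as determined by the treating investigator". Protocol 11.2.2.2.1 also makes a subject ineligible for touch-up after certain visual findings, including treatment-related abnormalities in visual function.

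**The concern.** Touch-up is the only subgroup in the SAP 6.2.1 list that is defined after treatment starts; the others are baseline characteristics. Two things follow from the rules alone, without any assumed rate.

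- **Dilution.** A TEAE between the first injection and Week 4 counts in the touch-up group if the subject is later touched up, although the touch-up cannot have caused it.
- **Selection on the outcome.** A subject whose early AE rules out touch-up falls in the no-touch-up group and brings that AE along. The visual findings that this trial monitors closely are among those sorted this way.

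At stake is how a reader interprets the table. Someone comparing the two columns to judge what a second injection adds would be comparing groups formed partly by the events being counted.

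**Working it through.** **The plan's own figure.** The only stated safety-size figure (Protocol 13.2, SAP 3) is an 80% chance of at least one AE with true probability 1.1% in 150 treated subjects. It reproduces: 1 − (1 − 0.011)^150 = 0.810. The documents give no figure for the touch-up subgroup, so every rate below is an assumption.

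**Illustration A.** Assumed inputs: 150 treated; 25% have a related TEAE before Week 4 (37.5 with, 112.5 without); touch-up is given to 50% of those without (56.25); touch-up causes a related TEAE in 15%; there are no other later events. Let g be the touch-up rate among subjects with an early AE.

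- Touch-up rate of TEAE = (37.5g + 0.15 × 56.25) / (37.5g + 56.25)
- No-touch-up rate of TEAE = 37.5(1 − g) / [37.5(1 − g) + 56.25]
- Share refused for an AE = 1 − g/0.5

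| Share refused | g | Touch-up | No touch-up | Difference (points) |
|---|---|---|---|---|
| 0% | 0.50 | 27.1875/75 = 36.25% | 18.75/75 = 25.0% | +11.25 |
| 10% | 0.45 | 25.3125/73.125 = 34.6% | 20.625/76.875 = 26.8% | +7.8 |
| 30% | 0.35 | 21.5625/69.375 = 31.1% | 24.375/80.625 = 30.2% | +0.8 |
| 60% | 0.20 | 15.9375/63.75 = 25.0% | 30/86.25 = 34.8% | −9.8 |

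Setting the two rates equal, with x = 37.5g, gives 104.0625x = 1318.36, so x = 12.67 and g = 0.338. The sign therefore reverses once about 32% of early-AE subjects are refused. With no refusals the sign is right, but the added 15 points shrink to 15 × (1 − 0.25) = 11.25.

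**Illustration B, allowing later events in both groups.** Assumed inputs: early AE risk a; share refused given an early AE q; touch-up rate if not refused t; later AE risk b = 10%, the same with or without an early AE; added risk from touch-up h = 10 points.

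- P(early AE | touch-up) = a(1 − q)/(1 − aq)
- P(early AE | no touch-up) = [a − a(1 − q)t] / [1 − (1 − aq)t]
- Planned Cycle 1 incidence = 1 − (1 − early)(1 − late), with late = b + h after touch-up and b otherwise

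For a = 0.2, q = 0.5, t = 0.5:
- early risks are 0.1/0.9 = 11.1% and 0.15/0.55 = 27.3%;
- planned table: 1 − 0.889 × 0.80 = 28.9% against 1 − 0.727 × 0.90 = 34.5%, a difference of −5.7 points;
- counting only onsets from the Week 4 decision: 20% against 10%, the true +10 points.

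With q = 0 the difference is h(1 − a): +8.0 points for a = 0.2 and +6.0 for a = 0.4. With q = 0.25 and t = 0.5 it is +1.2 points for a = 0.2 and −4.2 for a = 0.4. The refusal share needed for reversal therefore depends on the inputs. At 10% refusal, the added risk that would be exactly hidden runs from 1.3 points (a = 0.1, t = 0.3) to 11.0 points (a = 0.4, t = 0.7).

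**Forces the other way, in neither illustration.** Touched-up subjects have about four more weeks on study (76 against 72 in Protocol 8.1), because later visits are timed from the last injection. They also have extra visits V2-b/C2-b and V2-c/C2-c (SAP, disposition of subjects), so more events can be recorded. Subjects who drop out before Week 4 fall in the no-touch-up group with little follow-up.

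**The case against.** A reader might infer that the table is meant to measure the added risk of touch-up, and that a harmful touch-up would therefore look protective. The documents do not support either step. No section gives the table that purpose. It is one of seven descriptive subgroups, with no test, and can be read literally as Cycle 1 incidence by regimen received.

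Nor do the documents show that refusals are frequent. The rule concerns AEs that still exist and cause concern at Week 4, not any event since Day 1. Protocol 6.2 says that previously reported injection-site responses cleared within 14 days, and that many common treatment responses in the pilot resolved before a follow-up visit. Refusals may be few, and the table would then have the right sign.

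There are also partial safeguards. Protocol 13.4.2 summarises diary-recorded common treatment responses separately for the initial injection and its touch-up. SAP 6.2.1 flags, in the listing of related TEAEs, onset more than 28 days after the most recent injection. The SAP's extent-of-exposure text tabulates the reasons why touch-up was or was not done. Some SAP text is not visible, including material next to the subgroup list, so a further rule cannot be excluded.

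Most of this stands as a limit on size and importance. It does not remove either mechanism. The diary summaries do not cover investigator-reported TEAEs, the flag appears only in a listing, and the reasons are planned for TN, TC and TRT only and are not linked to TEAEs.

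**Conclusion.** The concern holds as a limitation of a descriptive safety table. Counting from the first injection dilutes any added risk of touch-up, and refusal for an AE biases the comparison towards touch-up looking safe. Both follow from the visible text.

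The net size and direction are unknown. Reversal of sign needs substantial refusal, about one third or more of early-AE subjects in illustration A. That threshold moves with the assumed early-AE risk, touch-up rate and true added risk, and longer follow-up and extra visits after touch-up work against it. It would be wrong to conclude that the table will make touch-up look protective; it may or may not.

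The overall incidence of related TEAEs, which is the secondary safety endpoint, is summarised in the whole safety population and is not affected. Neither is the primary endpoint.

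**What to change.** In SAP 6.2.1, keep the planned table, label it as incidence by regimen received, and state that it is not a comparison of touch-up risk. Add a table of TEAEs and related TEAEs by onset:

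1. onset before the touch-up, or before V2-a/C2-a if there was none, for all treated subjects;
2. onset on or after the touch-up, among subjects who received it;
3. onset on or after V2-a/C2-a, among subjects still in the study at that visit who had no touch-up, with those refused for an AE shown separately.

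Include DTN and DTC, and extend the summary of touch-up reasons to them if those reasons are recorded. State how a missed V2-a/C2-a is handled; the Day 29 target in SAP 6.4.1 is one option.

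This follows the plan's own logic, since SAP 6.2.1 already splits TEAEs by onset at retreatment. AE onset dates are already recorded (Protocol 12.1.2), and trial conduct does not change. The cost is SAP wording and additional overview and SOC/PT tables. Groups 2 and 3 remain non-randomised, because touch-up is discretionary and depends on AEs, so the new table is also descriptive.
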